# 5.3. Other Considerations for Data Analyses and Data Handling Conventions

Other considerations for data analyses and data handling conventions are outlined in the appendices:

Section	Component
10.1	Appendix 1: Schedule of Activities
10.2	Appendix 2: Study Phases and Treatment Emergent Adverse Events
10.3	Appendix 3: Data Display Standards & Handling Conventions
10.4	Appendix 4: Derived and Transformed Data
10.5	Appendix 5: Reporting Standards for Missing Data
10.6	Appendix 6: Division of AIDS (DAIDS) Table for Grading the Severity of Adult and Pediatric Adverse Events
10.7	Appendix 7: Values of Potential Clinical Importance

## 6. STUDY POPULATION ANALYSES

## 6.1. Overview of Planned Study Population Analyses

The study population analyses will be based on the "Safety" population, unless otherwise specified.

Study population analyses including analyses of participant's disposition, protocol deviations (including inclusion/exclusion criteria deviations), demographic and baseline characteristics, prior and concomitant medications, and exposure will be based on GSK Core Data Standards. Details of the planned displays are presented in Appendix 9: List of Data Displays.

## 7. PHARMACOKINETIC ANALYSES

## 7.1. Primary Pharmacokinetic Analyses

### 7.1.1. Endpoint / Variables

#### 7.1.1.1. Drug Concentration Measures

Refer to Appendix 3: Data Display Standards & Handling Conventions (Section 10.3.3 Reporting Standards for Pharmacokinetic). Plasma concentrations of GSK3640254, TAF, FTC, and TFV will be measured and reported.

#### 7.1.1.2. Derived Pharmacokinetic Parameters

Pharmacokinetic parameters will be calculated by standard non-compartmental analysis according to current working practices and using the currently supported version of WinNonlin (6.4 or higher). All calculations of non-compartmental parameters will be based on actual sampling times. Pharmacokinetic parameters listed will be determined from the plasma concentration-time data, as data permits.

Parameter	Parameter Description
Cmax	Maximum observed concentration, determined directly from the concentration-time data.
Сτ	Plasma concentration at the end of the dosing interval
AUC(0-τ)	Area under the plasma concentration-time curve from time 0 to the end of the dosing interval at steady state, to be calculated using the linear trapezoidal rule for each incremental trapezoid and the log trapezoidal rule for each decremental trapezoid.

#### NOTES:

Additional parameters may be included as required.

## 7.1.2. Summary Measure

Area under concentration-time curve (AUC(0- $\tau$ )), C $\tau$  and Cmax at steady state following doses of TAF/FTC 25/200 mg QD Days 1 through 14 in Period 1 and TAF/FTC 25/200 mg QD coadministered with GSK3640254 200 mg QD on Days 1 through 7 in Period 2 in healthy subjects.

### 7.1.3. Population of Interest

The primary pharmacokinetic analyses will be based on the PK concentration population for plasma PK concentrations and the PK parameter population for plasma PK parameters and statistical analysis.

## 7.1.4. Statistical Analyses / Methods

Details of the planned displays are provided in Appendix 9: List of Data Displays and will be based on GSK Data Standards and statistical principles.

Unless otherwise specified, endpoints / variables defined in Section 7.1.1 will be summarised using descriptive statistics, graphically presented (where appropriate) and listed.

Primary plasma PK parameters (AUC(0- $\tau$ ) and Cmax) will be estimated for TAF (Periods 1 and 2) and primary plasma PK parameters AUC(0- $\tau$ ), C $\tau$ , and Cmax will be estimated for FTC and TFV (Periods 1 and 2). Summary statistics (arithmetic mean, geometric mean, median, standard deviation, minimum, maximum, and coefficient of variation) for plasma TAF, FTC, and TFV PK parameter values will be summarized by treatment

### 7.1.4.1. Statistical Methodology Specification

The following PK statistical analyses will only be performed if sufficient data are available (i.e. if participants have well defined plasma profiles).

### **Endpoint / Variables**

Plasma primary PK endpoints include AUC(0-τ), Cτ and Cmax, as data permit

#### **Model Specification**

- Analyses will be performed on the natural logarithms of AUC(0-τ), Cτ and Cmax using linear mixed-effect models with period as a fixed effect, participants as random effect, and measurements within participant as repeated measures.
- Effects will be estimated, and CIs will be constructed for the following treatment comparisons: Period 2 versus Period 1 (TAF, FTC, and TFV)
- Point estimates and 90% CIs for treatment differences on the log scale derived from the model will be exponentiated to obtain estimates for geometric mean ratios and CIs on the original scale.

## **Model Checking & Diagnostics**

 Model assumptions will be applied, but appropriate adjustments may be made based on the data.

#### **Model Results Presentation**

• Statistical analysis by analysis of variance (ANOVA) will be presented in tabular format with geometric mean ratios for:

Period 2 versus Period 1 (TAF, FTC, and TFV)

## 7.2. Secondary Pharmacokinetic Analyses

#### 7.2.1. Endpoint / Variables

## 7.2.1.1. Drug Concentration Measures

Refer to Appendix 3: Data Display Standards & Handling Conventions (Section 10.3.3 Reporting Standards for Pharmacokinetic).

#### 7.2.1.2. Derived Pharmacokinetic Parameters

Pharmacokinetic parameters will be calculated by standard non-compartmental analysis according to current working practices and using the currently supported version of WinNonlin (6.4 or higher). All calculations of non-compartmental parameters will be based on actual sampling times.

Plasma pharmacokinetic parameters listed below will be determined from the total plasma concentration-time data, as data permits.

Parameter	Parameter Description
Cmax	Maximum observed concentration, determined directly from the concentration-time data.
	(GSK3640254 only)
Сτ	Plasma concentration at the end of the dosing interval (GSK3640254 only)
AUC(0-τ)	Area under the plasma concentration-time curve from time 0 to the end of the dosing
	interval at steady state, to be calculated using the linear trapezoidal rule for each
	incremental trapezoid and the log trapezoidal rule for each decremental trapezoid.
	(GSK3640254 only)
Tmax	Time to first occurrence of Cmax

#### NOTES:

Additional parameters may be included as required.

## 7.2.2. Summary Measure

Area under concentration-time curve [AUC(0- $\tau$ )], C $\tau$ , Cmax, and Tmax at steady state following doses of TAF/FTC 25/200 mg QD Days 1 through 14 in Period 1 and TAF/FTC 25/200 mg QD coadministered with GSK3640254 200 mg QD on Days 1 through 7 in Period 2 in healthy subjects.

### 7.2.3. Population of Interest

The secondary pharmacokinetic analyses will be based on the PK concentration population for plasma PK concentrations, and the PK parameter population for plasma and statistical analysis, unless otherwise specified.

### 7.2.4. Statistical Analyses / Methods

Details of the planned displays are provided in Appendix 9: List of Data Displays and will be based on GSK Data Standards and statistical principles.

Unless otherwise specified, endpoints/variables defined in Section 7.2.1 will be summarized using descriptive statistics, graphically presented (where appropriate) and listed.

Secondary plasma PK parameters (Tmax) will be estimated for TAF, FTC, and TFV (Periods 1 and 2) and secondary plasma PK parameters AUC(0- $\tau$ ), C $\tau$ , Cmax, and Tmax will be estimated for GSK3640254 (Period 2). Summary statistics (arithmetic mean, geometric mean, median, standard deviation, minimum, maximum, and coefficient of variation) for plasma GSK3640254 and TAF, FTC, and TFV PK parameter values will be summarized by treatment.

Predose (trough) PK plasma concentrations (TAF, FTC, and TFV: Days 2 through 14 [Period 1] and Days 1 through 7 [Period 2]; GSK3640254: Days 2 through 7 [Period 2]) will be summarized using the PK Concentration Population, and used to assess achievement of steady state.

## 8. SAFETY ANALYSES

The safety analyses will be based on the "Safety" population, unless otherwise specified.

## 8.1. Adverse Events Analyses

Adverse events analyses including the analysis of AEs, SAEs and other significant AEs will be based on GSK Core Data Standards. The details of the planned displays are provided in Appendix 9: List of Data Displays.

## 8.2. Clinical Laboratory Analyses

Laboratory evaluations including the analyses of chemistry laboratory tests, hematology laboratory tests, urinalysis, and liver function tests will be based on GSK Core Data Standards and will be graded using the Division of AIDS (DAIDS) Table for Grading the Severity of Adult and Pediatric Adverse Events (Version 2.1, July 2017). The details of the planned displays are in Appendix 9: List of Data Displays.

## 8.3. Other Safety Analyses

The analyses of non-laboratory safety test results including ECGs, vital signs, and Columbia Suicide Severity Rating Scale (C-SSRS) will be based on GSK Core Data Standards, unless otherwise specified. A figure of mean change from baseline in QTcF interval along with the 2-sided 95% CI using Student's t distribution will be presented by treatment and visit. The details of the planned displays are presented in Appendix 9: List of Data Displays.

## 10. APPENDICES

## 10.1. Appendix 1: Schedule of Activities

## 10.1.1. Protocol Defined Schedule of Events

## **Screening Visit**

Procedure	Screening (up to 28 days before Day 1)				
Outpatient visit	Х				
Informed consent	X				
Inclusion and exclusion criteria	X				
Demography	X				
Full physical examination including height and weight 	X				
Laboratory assessments (hematology, chemistry, urinalysis)	X				
12-lead electrocardiogram	X				
Vital sign measurements	X				
Medication/drug/alcohol history	X				
Past and current medical conditions	X				
Columbia Suicide Severity Rating Scale	X				
Serum pregnancy test	X				
Follicle-stimulating hormone (as needed, to confirm postmenopausal status)	Χ				
Drug, alcohol, and cotinine screen	X				
HIV, Hepatitis B and C screening	Х				

HIV = human immunodeficiency virus.

 A full physical examination will include at a minimum, assessments of the skin, cardiovascular, respiratory, gastrointestinal, and neurological systems.

## **Time and Events Table**

Period 1			Period 2								р	Notes			
Procedure	Day –1	Day 1-5	Day 6-13	Day 14	Day 1	Day 2	Day 3	Day 4	Day 5	Day 6	Day 7	Day 8	Day 9 	Day 10	
Admit to clinic	Х														
Discharge from clinic														Х	
Brief physical examination	X												Х		A brief physical examination will include, at a minimum, assessments of the skin, lungs, cardiovascular system, and abdomen (liver and spleen).
Vital sign measurements	Χ	Χ	D7		Χ			Χ			Х		Χ	Х	
Single 12-lead ECG	Х	D1			X			X			X		X		All ECGs in Period 1 and 2 will be pre-dose, post-dose at 2 hours, and post-dose 4 hours. The predose ECGs on Day 1 of both Period 1 and Period 2 will be taken in triplicate.
Drug, alcohol, and cotinine screen	Х														See Protocol Appendix 2 for specific tests to be performed.
Laboratory assessments (hematology, chemistry, urinalysis)	Х		D7	Х			Х				Х		Х		See Protocol Appendix 2 for specific tests to be performed.
Pregnancy test	Χ												Χ		
Columbia-Suicide Severity Rating Scale					Х						Х				

	Period 1			Period 2								p	Notes		
Procedure	Day -1	Day 1-5	Day 6-13	Day 14	Day 1	Day 2	Day 3	Day 4	Day 5	Day 6	Day 7	Day 8	Day 9 	Day 10	
Genetic sample (Optional)	Х														
Study intervention: TAF/FTC 25/200 mg		Х	Х	Х	Х	Х	Х	Х	Х	Х	Х				
Study intervention: GSK3640254 200 mg					Х	Х	Х	Х	Х	Х	Х				
TAF, FTC, and TFV serial PK sampling				х	х						х	Х			Blood collection for PK analysis of TAF, FTC, and TFV will be collected at 0.25, 0.5, 0.75, 1, 1.5, 2, 3, 4, 5, 6, 8, 12, and 24 hours postdose (Period 1, Day 14 and Period 2, Day 7).
TAF, FTC, and TFV trough PK sampling		D2-5	Х	Х	Х	Х	Х	Х	Х	Х	Х				Blood collection for TAF, FTC, and TFV trough PK samples will be collected on Period 1, Days 2 through 14 and Period 2, Days 1 through 7.
GSK3640254 serial PK sampling											Х	Х			Blood collection for PK analysis of GSK3640254 will be collected at 1, 2, 2.5, 3, 3.5, 4, 4.5, 5, 6, 8, 12, and 24 hours postdose (Period 2, Day 7).

	Period 1			Period 2							Follow-up			Notes	
Procedure	Day –1	Day 1-5	Day 6-13	Day 14	Day 1	Day 2	Day 3	Day 4	Day 5	Day 6	Day 7	Day 8	Day 91	Day 10	
GSK3640254 trough PK sampling						Х	Х	Х	Х	Х	Х				Blood collection for GSK3640254 trough PK samples will be collected on Period 2, Days 2 through 7.
AE review		←======→													
SAE review	←														
Concomitant medication review	+	=====			======	=====	======	=====	=====	=====	=====	=====	======	==->	

AE = adverse event; D = Day; ECG = electrocardiogram; FTC = emtricitabine; PK = pharmacokinetic; SAE = serious adverse event; TAF = tenofovir alafenamide; TFV = tenofovir; W = washout.

 Evaluations scheduled for Period 2, Day 9 will also be performed for participants who discontinue early.

# 10.2. Appendix 2: Study Phases and Treatment Emergent Adverse Events

## 10.2.1. Study Phases

Assessments and events will be classified according to the time of occurrence relative to study treatment start date(/time) and stop date(/time).

Study Phase	Definition
Pre-Treatment	Date and Time ≤ Study Treatment Start Date and Time
On-Treatment	Study Treatment Start Date and Time < Date and Time ≤ Study Treatment Stop Date and Time + 4 days
Post-Treatment	Date and Time > Study Treatment Stop Date and Time + 4 days

## 10.2.1.1. Study Phases for Concomitant Medication

Study Phase	Definition
Prior	If medication end date is not missing and is before Day -1 of Period 1
Concomitant	Any medication that is not a prior

#### NOTES:

 Please refer to Appendix 5: Reporting Standards for Missing Data for handling of missing and partial dates for concomitant medication. Use the rules in this table if concomitant medication date is completely missing.

## 10.2.2. Treatment Emergent Flag for Adverse Events

Flag	Definition
Treatment Emergent	
 
If AE onset date and time is on or after treatment start date and time & on or before treatment stop date and time + 4 days.
 
Study Treatment Start Date and Time ≤ AE Start Date and Time ≤ Study Treatment Stop Date and Time + 4 days.
 
If the AE onset date is completely missing, the AE is considered as treatment emergent.
 

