### **Objectives and Endpoints:**

Objective	Endpoint					

 
Primary
 
To assess the effect of GSK3640254 on the PK of TAF, FTC, and the active metabolite of TAF prodrug, TFV under fed conditions in healthy participants
 
	
 
AUC(0-τ) and Cmax for TAF
 
AUC(0-τ), Cmax, and Cτ for FTC and TFV
 
					

 
Secondary
 
To assess the safety and tolerability of TAF/FTC administered alone and when coadministered with GSK3640254 in healthy participants
 
	
 
Safety and tolerability parameters for AEs/SAEs, observed and change from baseline clinical laboratory assessments, ECGs, and vital sign measurements
 
					
• To characterize the steady-state PK of GSK3640254 in the presence of TAF/FTC in healthy participants	
 
AUC(0-τ), Cmax, Cτ, and Tmax for GSK3640254
 
					
• To characterize the steady-state PK of TAF, FTC, and TFV alone and in combination with GSK3640254 in healthy participants	
 
Tmax for TAF, FTC, and TFV
 
					

AE = adverse event; AUC  $(0-\tau)$  = area under the plasma concentration-time curve from time 0 to the end of the dosing interval at steady state; Cmax = maximum observed concentration; C $\tau$  = Plasma concentration at the end of the dosing interval; ECG = electrocardiogram; FTC = emtricitabine; PK = pharmacokinetics; SAE = serious adverse event; TAF = tenofovir alafenamide; TFV = tenofovir; Tmax = time of maximum observed concentration.

**Overall Design:** This is a Phase 1, open-label, fixed-sequence 2-period, one-way drug interaction study designed to assess the pharmacokinetics (PK), safety, and tolerability of GSK3640254 and TAF/FTC when administered alone and in combination in healthy participants.

The study will consist of a screening period and 2 sequential treatment periods. Participants will be screened with 28 days before the first dose of study intervention.

There is no washout between the last dose of study intervention in Period 1 and initiation of study intervention in Period 2. The participants will fast overnight for at least 8 hours prior to dosing and will receive the moderate fat meal 30 minutes prior to dosing. Participants will eat this meal in 30 minutes or less. Dose administration will occur within 5 minutes of completion of meal consumption.

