# 4. STUDY DESIGN

# 4.1. Overall Design

This is a Phase 1, open-label, fixed-sequence 2-period, one-way drug interaction study designed to assess the PK, safety, and tolerability of GSK3640254 and TAF/FTC when administered alone and in combination in healthy participants.

The study will consist of a screening period and 2 sequential treatment periods. Participants will be screened within 28 days before the first dose of study intervention. The treatments will be as follows:

- Treatment A: TAF/FTC 25/200 mg QD on Days 1 through 14 (Period 1)
- Treatment B: TAF/FTC 25/200 mg QD coadministered with GSK3640254 200 mg QD on Days 1 through 7 (Period 2)

There is no washout between the last dose of study intervention (Treatment A) in Period 1 and initiation of study intervention (Treatment B) in Period 2. The participants will fast overnight for at least 8 hours prior to dosing and will receive a moderate fat meal 30 minutes prior to dosing. Participants will eat this meal in 30 minutes or less. Dose administration will occur within 5 minutes of completion of meal consumption.

Pharmacokinetic blood samples for analysis of TAF, FTC, and TFV will be collected before dosing (0 hour) on Days 2 through 14 (Period 1) and Days 1 through 7 (Period 2) and up to 24 hours after TAF/FTC dosing on Period 1, Day 14 and Period 2, Day 7. Pharmacokinetic blood samples for analysis of GSK3640254 will be collected before dosing (0 hour) on Days 2 through 7 (Period 2) and up to 24 hours after GSK3640254 dosing on Day 7.

Safety and tolerability will be assessed by monitoring and recording of AEs, clinical laboratory test results, vital sign measurements, 12-lead ECG results, and physical examination findings.

Study assessments will be performed as indicated in the Schedule of Activities (SoA) (Section 1.3). Participants will be confined to the clinic from Day –1 until discharge on Period 2, Day 10.

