# 5. CONSIDERATIONS FOR DATA ANALYSES AND DATA HANDLING CONVENTIONS

## 5.1. Study Treatment & Sub-group Display Descriptors

Treatment Group Descriptions									
Data Displays for Reporting									
Description Code Order in TLF									
TAF/FTC 25/200 mg QD on Days 1 through 14 in Period 1	TAF/FTC	1							
TAF/FTC 25/200 mg QD + GSK3640254 200 mg QD on Days 1 through 7 in Period 2	TAF/FTC+GSK3640254	2							

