## 10.5.2.1. Handling of Missing and Partial Dates

Reporting Detail
Partial dates will be displayed as captured in participant listing displays.

 
The eCRF allows for the possibility of partial dates (i.e., only month and year) to be recorded for AE start and end dates; that is, the day of the month may be missing. In such a case, the following conventions will be applied for calculating the time to onset and the duration of the event:         
 
Missing Start Day: First of the month will be used unless this is before the start date of study treatment; in this case the study treatment start date will be used and hence the event is considered On-treatment as per Appendix 2: Study Phases and Treatment Emergent Adverse Events.
 
Missing Stop Day: Last day of the month will be used, unless this is after the stop date of study treatment; in this case the study treatment stop date will be used.
 
 
 

 
Completely missing start or end dates will remain missing, with no imputation applied.
 
Consequently, time to onset and duration of such events will be missing.
 

 
Partial dates for any concomitant medications recorded in the eCRF will be imputed using the following convention:
 
If the partial date is a start date, a '01' will be used for the day and 'Jan' will be used for the month
 
If the partial date is a stop date, a '28/29/30/31' will be used for the day (dependent on the month and year) and 'Dec' will be used for the month.
 
The recorded partial date will be displayed in listings.
 

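### With no washout, does the treatment stop + 4 days window put combination-period adverse events in the TAF/FTC-alone column?

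*SAP*

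**What the plan says.** The treatment-emergent flag in SAP 10.2.2 is "Study Treatment Start Date and Time ≤ AE Start Date and Time ≤ Study Treatment Stop Date and Time + 4 days". SAP 10.2.1 defines the on-treatment phase by almost the same interval: "Study Treatment Start Date and Time < Date and Time ≤ Study Treatment Stop Date and Time + 4 days". Both refer only to study treatment. Neither mentions a period, and neither cuts the window at the start of the next treatment.

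The design runs the two treatments back to back. The Protocol synopsis states: "There is no washout between the last dose of study intervention in Period 1 and initiation of study intervention in Period 2". TAF/FTC alone is given on Period 1 Days 1 to 14 and the combination on Period 2 Days 1 to 7 (Protocol 4.1).

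SAP 5.1 gives two display columns, each tied to a period; the second is "TAF/FTC 25/200 mg QD + GSK3640254 200 mg QD on Days 1 through 7 in Period 2". Three further SAP rules bear on the question:

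- Safety baselines are set for each period (SAP 5.2).
- Data are reported by the treatment actually received, unless otherwise stated (SAP 10.3.2, Formats).
- Period Day restarts at the first Period 2 dose (SAP 10.4.1).

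For an AE whose start day is unknown, SAP 10.5.2.1 uses the first of the month. If that falls before dosing began, "in this case the study treatment start date will be used".

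**The concern.** A lag after the last dose is harmless when a washout follows. Here the next treatment starts one day later. If treatment stop is taken as the last dose of TAF/FTC alone, an AE beginning in the first days of GSK3640254 dosing satisfies the TAF/FTC-alone window as well as the combination window. By calendar date this touches Period 2 Days 1 to 4, which is 4 of 7 dosing days (57%).

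The error would run one way. Events on the combination would raise the rate under TAF/FTC alone and make GSK3640254 look better tolerated than it is. The secondary safety objective rests on those two columns, and the protocol names gastrointestinal and neuropsychiatric events among the main risks. With about 16 participants, one additional affected participant moves a column percentage by 1/16, about 6 points.

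The partial-date rule seems to lean the same way, since it tends to place an unknown start day early, and so in Period 1.

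**Working it through.** **Timeline check.** Screening of 28 days, Period 1 of 14 days and Period 2 to discharge on Day 10 give 28 + 14 + 10 = 52 days. This is the duration stated in the synopsis, and it leaves no gap between periods.

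**Clock.** Assume doses 24 h apart, with the Period 1 Day 1 dose at hour 0.

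| Event | Hour |
|---|---|
| Period 1 Day 14 dose | 13 × 24 = 312 |
| Period 2 Day 1 dose | 14 × 24 = 336 |
| Period 2 Day 7 dose | 20 × 24 = 480 |
| Period 2 Day 10, dose clock time | 23 × 24 = 552 |

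**Whole-study reading.** Treatment stop is hour 480, and the window ends at 480 + 96 = 576 h. That is (576 − 336)/24 + 1 = Period 2 Day 11, after discharge. One window covers every AE collected from first dose to discharge. There is no second window, so the overlap is 0 h.

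**Per-treatment reading.** The TAF/FTC-alone window ends at 312 + 96 = 408 h, which is the time of the Period 2 Day 4 dose.

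- Overlap after the first GSK3640254 dose: 408 − 336 = 72 h, or 3 of 7 dosing intervals (43%).
- Share of the TAF/FTC-alone window: 408/24 = 17 days, so 3/17 = 18%.
- Share of the combination window: (576 − 336)/24 = 10 days, so 3/10 = 30%.
- Share of the combination window observed to discharge: (552 − 336)/24 = 9 days, so 3/9 = 33%.
- If the Period 2 Day 1 dose moves by 2 h either way, the overlap is 70 to 74 h.

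The calendar-date count of 4/7 = 57% (or 4/10 = 40% of Period 2 Days 1 to 10) arises only if times are ignored. The rule is written in date and time.

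**Which reading the text supports.** SAP 5.2 and the Period Day rule in SAP 10.4.1 name the period explicitly; SAP 10.2.1 and 10.2.2 do not. TAF/FTC dosing also continues daily through Period 2 Day 7, so nothing stops at Period 1 Day 14. The whole-study reading is the natural one.

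**Which column an AE falls in.** The flag decides whether an AE is treatment-emergent, not which treatment it belongs to. SAP 5.1 limits the TAF/FTC column to Period 1. SAP 10.3.2 reports by treatment received, and a participant with an AE on Period 2 Day 2 is receiving the combination. SAP 10.4.1 counts that day from the first Period 2 dose. Together these lead to attribution by treatment at onset.

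**Partial dates.** The convention in SAP 10.5.2.1 is there to compute time to onset and duration; it assigns no column. Participants are confined from Day −1 to Period 2 Day 10, so an unknown start day should be rare.

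**The case for a change.** The strongest reply is that the SAP falls short on either reading. Per treatment, the windows overlap. For the whole study, the flag cannot fill two columns, and no sentence says how they are filled. The rule on treatment received is a general formatting convention that does not mention AE onset or the 4-day lag. Period Day is only a day count and is not linked to AE tables. Two programmers could in principle produce different tables, and any double counting would favour GSK3640254. In dogs, gastrointestinal signs began on the first day of dosing (Protocol 2.3.1), which would fall within the affected days. SAP 10.2.1 also allows a date without a time, and a date-only comparison brings back the fourth day.

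Part of this stands: there is no explicit attribution sentence, and an imputed start date, if it were used for attribution, would tend towards Period 1. The rest carries less weight. The period-defined columns and the reporting rule make double counting the less natural implementation. Even under double counting the combination column stays complete, because events are added to the other column and not moved. A share of 30 to 33% of combination events counted twice also needs a constant hazard. The documents give no human onset data to support that, and exposure roughly doubles with repeat dosing (Protocol 2.2), so the hazard need not be constant.

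**Conclusion.** The concern does not call for a change. The SAP omits a detail that analysts would fill sensibly: an AE goes to the treatment being taken when it starts. On the natural reading of SAP 10.2.1 and 10.2.2 the overlap is 0 h. On the less natural per-treatment reading it is 72 h (3 of 7 dosing intervals), or up to 4 calendar days if times are ignored, assuming doses 24 h apart.

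The consequences are small in either case. Protocol 9.4.2 plans no formal safety analysis, so no test or interval comparing AE rates depends on the window. All AEs are listed individually (SAP 10.9.9), so an event's onset can be checked against the dosing dates. The primary pharmacokinetic comparison does not use the window. A sentence on attribution would record what the existing rules already imply and would not be expected to alter a table. The conclusion rests on reading study treatment as the whole course of dosing. The sponsor's internal display standards, which the SAP cites for its AE tables, could not be examined.
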